Appendix 2 Schedule of Pharmacokinetic Blood [REDACTED] Samples

Procedure		Blood sampling for balovaptan and M2, M3 metabolites							Blood sampling for ¹³ C-balovaptan		[REDACTED]	
		Period 1	Period 2							Period 1	Period 2	Period 2
Study Day		1	1	2	7	8	12	13	14	1	14	12
Predose		X	X	X	X	X	X	X	X			
Hours Post Oral Dose	0.25	X										
	0.5	X							X			
	1	X							X			
	1.25	X							X	X ^a	X ^a	
	1.33	X							X	X	X	
	1.5	X							X	X	X	
	1.75	X							X	X	X	
	2	X			X				X	X	X	
	2.25	X							X	X	X	
	2.5	X							X	X	X	
	3	X			X				X	X	X	X ^b
	3.5	X							X	X	X	
	4	X			X				X	X	X	
	4.5	X							X	X	X	
	5	X							X	X	X	
	6	X			X				X	X	X	
	8	X							X	X	X	
	12	X			X				X	X	X	
	16 (P1/D2 or P2/D15)	X (D2)				X			X (D15)	X	X (D15)	
	24 (P1/D2 or P2/D15)	X (D2)							X (D15)	X	X (D15)	
	48 (P1/D3 or P2/D16)	X (D3)							X (D16)	X	X (D16)	
60 (P1/D3 or P2/D16)	X (D3)							X (D16)	X	X (D16)		
72 (P1/D4 or P2/D17)	X (D4)							X (D17)	X	X (D17)		
96 (P1/D5 or P2/D18)	X (D5)							X (D18)	X	X (D18)		
108 (P1/D5 or P2/D18)	X (D5)							X (D18)	X	X (D18)		
120 (D6)	X (D6)											
144 (D7)	X (D7)											
168 (D8)	X (D8)											
192 (D9)	X (D9)											
216 (D10)	X (D10)											

Appendix 2

Schedule of Pharmacokinetic Blood and CSF Samples (cont.)

[REDACTED]; P1 = Period 1; P2 = Period 2.

^a Sample to be taken as shortly as possible prior to start of intravenous infusion.

[REDACTED]

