3. STUDY DESIGN

3.1 DESCRIPTION OF THE STUDY

This study will be a non-randomized, open-label, parallel group, two-treatment study in healthy volunteers to investigate the absolute oral bioavailability of balovaptan. The study will be conducted at 1 site in the Netherlands.

Screening

Screening will be conducted up to 28 days prior to admission to the clinical research unit (CRU).

In-Clinic Confinement

Subjects will be in the CRU for 2 study periods. In both periods, subjects will be admitted on Day -1 (the day before dosing begins). Day 1 will be the first day of dosing. In Period 1, subjects will be discharged on Day 10 after all assessments have been completed. There will be a wash-out period of 14 days between Day 1 of Period 1 and Day 1 of Period 2.

Subjects will be readmitted to the CRU for a second in-house period on Day 14 of Period 1 (Day -1 of Period 2) to begin Period 2. Day 1 will be the first day of dosing. In Period 2, subjects will be discharged in the morning of Day 19.

During the in-house stays and screening and follow-up visits, subjects will undergo assessments as outlined in the schedule of activities ([Appendix 1](#)), including assessments of AEs and concomitant medications, vital signs, electrocardiograms (ECGs), clinical laboratory evaluations, and blood sampling for PK evaluations. ■

Dosing

Two cohorts of 8 subjects each will be included in the study. The 2 cohorts will receive the following treatment regimens:

Cohort 1

Period 1:

- Day 1: a single oral dose of 10 mg balovaptan after at least 10 hours of fasting, followed 1.25 hours later by a 15-minute intravenous (IV) infusion of [¹³C]-labeled balovaptan 0.1 mg.

Period 2:

- Day 1 to Day 14: oral doses of 10 mg balovaptan QD; on Day 7 and Day 14 study drug administration will take place after at least 10 hours of fasting.
- Day 14: the final oral dosing will be followed 1.25 hours later by a 15-minute IV infusion of [¹³C]-labeled balovaptan 0.1 mg.

Cohort 2

Period 1:

- Day 1: a single oral dose of 50 mg balovaptan after at least 10 hours of fasting, followed 1.25 hours later by a 15-minute IV infusion of [¹³C]-labeled balovaptan 0.1 mg.

Period 2:

[figure not shown]
- Day 1 to Day 14: oral doses of 50 mg balovaptan QD; on Day 7 and Day 14 study drug administration will take place after at least 10 hours of fasting.
- Day 14: the final oral dosing will be followed 1.25 hours later by a 15-minute IV infusion of [¹³C]-labeled balovaptan 0.1 mg.

Follow-up

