3.3.2 Rationale for Balovaptan Dose and Schedule

A dose of 10 mg balovaptan has shown statistically significant changes in efficacy parameters in patients with ASD and is the current recommended Phase 3 dose.

In addition, a dose of 50 mg balovaptan will be studied as well to investigate any dose-dependent changes in oral bioavailability. In the MAD part of study BP25694, multiple doses of 52 mg QD in healthy subjects were well tolerated and resulted in a C_{max} of 484 ng/mL, [REDACTED]. Thus, a dose of 50 mg balovaptan QD is considered suitable to study dose-dependent changes in oral bioavailability.

Balovaptan is being developed for use in ASD, so it is expected that patients will need to take it for prolonged periods of time, likely for years or for life. Hence multiple dose testing is relevant from a clinical point of view. The multiple dose PK of balovaptan with 14 days of dosing was previously characterized in humans and was found to be time-dependent. Accumulation was observed with multiple dosing, and steady state of balovaptan was observed after approximately 7 days of dosing and after 10 days for M3. The plasma PK time course of M2 has not been closely studied but steady state has been demonstrated after 2 weeks of QD dosing with balovaptan 10 mg. Based on these observations, a dosing period of 14 days has been selected to ensure steady state plasma levels of balovaptan and its major metabolites M2 and M3 are reached and to maximize the possibility to observe any time-dependent changes in PK.

The microdose of [¹³C]-labeled balovaptan has been set to 0.1 mg; 0.1 mg is the maximum allowed IV microdose that can be administered without IV toxicity studies. Exposure after an 0.1-mg IV dose is covered by the existing nonclinical toxicity and PK

data. The t_{max} following oral dosing in the fasted state is expected to be approximately 1.5 hours postdose after a single dose and approximately 3 hours after multiple doses. To have the end of the infusion and the t_{max} of [^{13}C]-labeled balovaptan coincide with the t_{max} of the orally administered unlabeled balovaptan after a single dose, the 15-minute infusion of the microdose of [^{13}C]-labeled balovaptan will be started at 1.25 hours. For consistency the time of infusion is similar after the (last) multiple oral dose when due to accumulation plasma levels of balovaptan are predicted to not be lower than at t_{max} after the single dose.

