### 9.2.3 Common Variable Derivations

Variable	Data Type	Definition/Calculation	Note
Change from Baseline	All	Post-dose Observation minus Baseline Observation	
Analysis Period	All	Time period starting 1 day before dosing of each of the treatments and ends 1 day before dosing in next analysis period or at the start of the follow-up period for the last treatment.	
Analysis Study Day (Prior to first Dose)	All	Date of Measurement minus Dose Date	
Analysis Study Day (Post first Dose)	All	Date of Measurement minus Dose Date +1	

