**Table 1: Plasma Parameters**

Parameter	Description	Analyte/Analysis Period	SAS Programming Notes
C max	Maximum plasma concentration. Observed peak analyte concentration obtained directly from the experimental data without interpolation, expressed in concentration units	All analytes	C max from WNL
C trough	Concentration at the end of the dosing interval (tau)	All analytes/ Period 2	The concentration at 24 h calculated in SAS
C last	Last measurable plasma concentration	All analytes	Calculated in SAS
t max	Time to maximum plasma concentration. First observed time to reach peak analyte concentration obtained directly from the experimental data without interpolation, expressed in time units.	All analytes	T max from WNL
AUC 0-last	Area under the concentration-time curve (time 0 to time of last quantifiable concentration).	All analytes/ Period 1	AUC last from WNL
AUC 0-inf	Area under the serum concentration-time curve (time 0 to infinity). Percent extrapolation less than or equal to 20% is required to obtain a reliable AUC inf .	All analytes/ Period 1	AUC INF_obs from WNL If AUC_%Extrap_obs >20% then parameter is not included
AUC 0-24h	Area under the serum concentration-time curve from time 0 to 24 hours post-dose	All analytes/ Period 1 and 2	AUC 0-24 from WNL where partial time =24, if missing for a subject then AUC at nominal time 24 hr from summary file is used for AUC 0-24
λ z	Terminal phase rate constant calculated by linear regression of the terminal log-linear portion of the concentration vs. time curve. Linear regression of at least three points and an adjusted R  greater than 0.70 are required to obtain a reliable λ z .	All analytes	Lambda_z from WNL If adjusted R  ≤ 0.7 the parameter is not estimated
t 1/2	Terminal phase half-life expressed in time units. Percent extrapolation <20% and adjusted R  greater than 0.7 is required to obtain a reliable t 1/2 .	All analytes	HL_Lambda_z from WNL If adjusted R  ≤ 0.7 the parameter is not estimated
t last	Time of last measurable plasma concentration	All analytes	Determined in SAS
R AUC	Accumulation ratio for AUC 0-24h	All analytes	Day 14 AUC 0-24h Period 2/ Day 1 AUC 0-24h Period 1 Calculated in SAS

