### 16.2.2 Pharmacokinetic Parameters

Plasma PK parameters for balovaptan, [C]-balovaptan, M2 and M3, will be estimated using non-compartmental methods with WinNonlin®.

The plasma PK parameters will be estimated from the concentration-time profiles. In estimating the PK parameters, BQL values will be set to zero for the pre-dose PK sample, as well as for all other samples being BLQ and occurring before  $t_{max}$ . For subsequent time points, the result will be set to missing. Actual sampling times, rather than scheduled sampling times, will be used in all computations involving sampling times. If the actual time or dose time is missing, the scheduled time may be substituted in order to calculate the PK parameter.

Descriptive statistics (number of subjects, arithmetic mean, geometric mean, SD, geometric and arithmetic CV, median, min, and max) will be used to summarize the calculated PK parameters by treatment, day and analyte. For  $t_{max}$ , only median, min and max will be presented.

The points to be included in the  $\lambda z$  range will be determined by the pharmacokineticist after inspection of the semi-log concentration-time profiles. At least 3 points will be required to be used and the range should ideally be spread over a time interval representing at least 2 half-lives. The  $C_{max}$  data point will not be included.

Parameters based on  $R^2$  below 0.70 or %AUCextra above 20% will be flagged and excluded from descriptive statistics.

The ratio of geometric means from the microdose IV kinetics with that from the oral dose will be estimated using an analysis of variance (ANOVA) of the natural logarithm transformed clearance (CL and CL/F). A mixed model will be used, separately for the 2 cohorts with the 2 doses of 10mg and 50mg, and will include fixed effects for route (oral or iv) and for day (1 and 14) and a random effect for subject. From this model the least-squares means (LSMeans) for clearance (CL) of [C]-balovaptan iv and for CL/F of oral balovaptan will be presented. The ratios of the LSMeans for the comparison of CL to CL/F (IV/Oral) will be obtained by exponentiating the difference of the LSMeans on the log scale. A 90% confidence interval for the ratios of the treatment means will be calculated.

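### Single-dose M2 and M3 profiles stop at 216 h although a usable 336 h sample is already scheduled, so slow eliminators may lose AUC0-inf under the SAP's 20% rule

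*Protocol*

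**What the plan says.** The sampling grid (Protocol Appendix 2, repeated in SAP Appendix 3) has columns headed "Blood sampling for balovaptan and M2, M3 metabolites". The Period 1 column ends at 216 h (Day 10). The predose row is also marked for Period 2 Day 1.

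Protocol 3.1 fixes the interval: "There will be a wash-out period of 14 days between Day 1 of Period 1 and Day 1 of Period 2". No study drug is given between the two.

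SAP 9.2.3 defines an analysis period as "Time period starting 1 day before dosing of each of the treatments and ends 1 day before dosing in next analysis period". The Period 2 Day 1 predose sample is drawn on the dosing day, so this rule puts it in Analysis Period 2. SAP Table 1 assigns AUC0-last and AUC0-inf to Period 1 only. No text adds the sample to the Period 1 profile.

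For AUC0-inf, the programming note in SAP Table 1 reads "If AUC_%Extrap_obs >20% then parameter is not included". SAP 16.2.2 adds that parameters with an extrapolated share "above 20% will be flagged and excluded from descriptive statistics". Table 1 also asks for less than 20% extrapolation before t1/2 is considered reliable.

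On the speed of the metabolites, Protocol 3.3.2 says that "steady state of balovaptan was observed after approximately 7 days of dosing and after 10 days for M3". For M2 it says only that steady state has been shown after two weeks of 10 mg daily.

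**The concern.** A sample drawn 336 h after a single dose, before any further dose, can only measure the tail of that dose. It is a valid last point of the single-dose profile, and it is already scheduled for the right analytes.

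M3 is slower than the parent to reach steady state, and little is known about M2, so these are the analytes for which a short profile could matter. The 20% rule acts on individuals, and it removes those with the longest half-lives first, who tend also to have the largest AUC. Any exclusions would leave the M2 or M3 AUC0-inf summary with fewer subjects and biased low. AUCinf and t1/2 of M2 and M3 are named secondary endpoints. Each cohort enrols 8, with a target of at least 6 evaluable for the primary PK analysis, so one or two lost values are a visible share.

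**Working it through.** **The plan's own figures.** The documents state no extrapolated percentage to reproduce. Their one sample-size figure, the precision factor, does reproduce: exp(2.015 × 0.35 × √(2/6)) = 1.50. It concerns CL versus CL/F and is untouched by this point.

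**Inputs from the documents.** Last Period 1 sample 216 h; next sample 14 × 24 = 336 h; limit 20%; parent half-life about 46 h (Protocol 1.2.1.1, Day 14); parent accumulation about 4-fold at 12 mg and 2-fold at 52 mg; M3 steady state after 10 days (240 h); M2 steady state by 14 days (336 h).

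**Assumptions.** Linear kinetics; metabolite formed from parent by a first-order process; metabolite half-life and its spread between subjects.

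**Parent.** The share beyond time T is 2^(−T/t½). At 46 h it is 3.9% at 216 h and 0.6% at 336 h. A 4-fold accumulation implies 24 × ln 2 / −ln(1 − 1/4) = 57.8 h, which gives 7.5% and 1.8%.

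**Metabolite.** With rate constants kp (parent) and km (metabolite), the share of AUC beyond T is

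f(T) = [kp·exp(−km·T) − km·exp(−kp·T)] / (kp − km).

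By superposition, the fraction of steady state reached after dosing for time T is 1 − f(T). The 10-day statement for M3 therefore calibrates km: set f(240) to 0.10 or 0.05 with the parent at 46 h.

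| M3 steady state attained at 240 h | Implied metabolite t½ | f(216) | f(336) |
|---|---|---|---|
| 90% | 39.5 h | 13.6% | 2.8% |
| 95% | 21.5 h | 7.2% | 1.2% |

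A typical M3 profile thus has about 7–14% extrapolated now and 1–3% with the extra sample. With a 46 h parent, 20% is crossed at a metabolite half-life of about 54 h.

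**M2, upper bound.** Suppose steady state is reached only at 336 h, and treat the tail as mono-exponential. The half-life is 336/log2(10) = 101 h (90% attained) or 336/log2(20) = 78 h (95%). The share beyond 216 h is 22.8% or 14.6%; beyond 336 h it is 10% or 5%.

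**Individuals.** I drew independent log-normal half-lives for parent (median 46 h) and M3, with 30% CV on each, and counted subjects with f above 20%.

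| Median M3 t½ | Over 20% at 216 h | Expected of 8 | Over 20% at 336 h |
|---|---|---|---|
| 21 h | 5% | 0.4 | 0.0% |
| 33 h | 16% | 1.3 | 0.1% |
| 39 h | 25% | 2.0 | 0.3% |

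At the 33 h median, a 42% CV (the plan's between-subject figure for CL/F, used as a proxy) gives 25% at 216 h and 1.6% at 336 h.

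**Observed versus true share.** The SAP tests the extrapolation from the fitted lambda-z. A metabolite curve still bending at 216 h gives too small a lambda-z. With a 46 h parent and a 36 h metabolite, a noise-free fit over 120–216 h gives 14.3% against a true 12.1%; a fit over 168–336 h gives 2.6% against 2.4%. The figures above are thus slightly favourable to the present plan.

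**The case against.** **A stronger reading is tempting but not supported.** A reader might infer that metabolite AUC0-inf generally sits at the 20% limit and that many subjects will be dropped. Metabolite half-lives of 36–72 h with a 46 h parent do give 12–28% beyond 216 h, and at 30% CV 19–81% of subjects over the limit. But half-lives of 46, 60 and 72 h imply only 88%, 82% and 77% of steady state at day 10. That conflicts with the protocol's statement on M3. The range could apply only to M2, for which the documents do not settle the matter.

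**The 58 h parent scenario is weak.** It turns accumulation into a half-life as if kinetics were linear and constant over time, yet Protocol 3.3.2 calls multiple-dose PK time-dependent. The same arithmetic at 52 mg gives 24 h, and then metabolite half-lives of 36–72 h give only 4–19%. The caveat about linearity also applies to the calibration used here.

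**The consequence is limited.** A subject over the limit still contributes AUC0-last, AUC0-24h, Cmax, Ctrough and the accumulation ratios. This stands.

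**The pharmacokineticist might use the sample anyway.** SAP 16.2.2 leaves the lambda-z points to judgement, and SAP 3.0 allows changes without a new SAP version. Nothing expressly bars the sample. But SAP 9.2.3 files it under Period 2, and a choice made after seeing the profiles is weaker than one stated beforehand.

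**The 336 h value may be BQL.** No LLOQ is given, so this stands as a limit on the gain. Slow eliminators, however, are the subjects most likely to be quantifiable at that time.

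**Conclusion.** The point holds for M2 and M3 as a possible, not a certain, loss. The single-dose profile ends at 216 h, a later sample of the same dose is scheduled, and the SAP's period definition leaves it out. A typical M3 profile is below the limit. Slow eliminators may cross it, and M2 might be near it if its steady state comes as late as 14 days. Any exclusions would bias the metabolite AUC0-inf summary low.

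These sizes rest on linear kinetics, a 46 h multiple-dose parent half-life applied to a single dose, the reading of M3 steady state as 90–95% attained, an assumed CV, and a quantifiable 336 h concentration.

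Two further inferences should be avoided. Oral balovaptan is not at risk. The primary endpoint is not affected either: metabolite AUC does not enter F, CL or CL/F, and the small change in parent extrapolation hardly moves oral AUC0-inf. Nor does the sample help the intravenous side, because the [13C]-balovaptan columns stop at 108 h and have no Period 2 Day 1 predose draw. Priority is low to moderate, for secondary endpoints only.

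**What to change.** State in SAP 16.2.2 and Appendix 3 that the Period 2 Day 1 predose sample, at its actual time (about 336 h), is also the last Period 1 sample for balovaptan, M2 and M3 when lambda-z, t1/2 and AUC0-inf are estimated. It remains the Period 2 predose value as well.

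Add a BQL rule for this sample. SAP 16.2.2 sets a BQL predose value to zero and a BQL value after tmax to missing. In the Period 1 profile the sample should count as post-tmax, so a BQL result is missing there and not zero.

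The cost is SAP wording and one programming rule, settled before database lock, with no new sample, assay or visit. There are two drawbacks. The last point follows a gap of 336 − 216 = 120 h. AUC0-last may also run to 336 h in some subjects and 216 h in others, so t_last should be reported beside it.

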1.2.1.1 Clinical Pharmacology

Plasma exposure of balovaptan increased in a greater than dose-proportional manner following single doses of 0.5 to 76 mg, whereas an approximately linear increase in exposure was observed after repeated dosing with 12 to 52 mg once daily (QD) for 14 days.

Balovaptan was rapidly absorbed with a median time to maximum observed plasma concentration (t_{max}) between 1 and 4.5 hours after administration of single doses in fasted state and between 3 and 4 hours following multiple dosing in fed state. Steady state was achieved after approximately 7 days, with an accumulation of approximately 4-fold after 12 mg QD and 2-fold after 52 mg QD; the mean apparent elimination half-life after the last dose (Day 14) was approximately 46 hours. Food had no relevant effect on the overall plasma area under the plasma concentration-time curve (AUC) of balovaptan.

In the human mass balance study (Study BP29279), an almost complete absorption of the study drug was observed within the first 72 hours following administration.

In plasma, steady state exposure to the [REDACTED] metabolite M3 was similar to or slightly higher than that of balovaptan and exposure to the [REDACTED] metabolite M2 was lower than that of parent. M3 and M2 qualify as major metabolites in plasma.

[REDACTED]

[REDACTED]

[REDACTED]

[REDACTED]

Hepatic metabolism was found to be the major pathway of elimination with the primary route of excretion via urine (approximately 53% of the material recovered, mostly

composed of metabolites). A further 30% of the administered dose was recovered in feces. The majority of excretion occurred within the first 7 days.

There was no clinically/statistically relevant PK interaction with the P-gp substrate risperidone, one of only 2 approved medications for ASD symptoms in the US, and fluoxetine, a weak CYP3A4 inhibitor often used to treat associated symptoms of ASD. Administration of a single dose of balovaptan 12 mg in combination with itraconazole, a strong CYP3A4 inhibitor, resulted in an increase in the exposure of balovaptan by 36% for maximum observed plasma concentration (C_{max}) and an approximately 3.1-fold increase for area under the concentration curve from time 0 to 120 hours (AUC_{0-120h}).

[REDACTED]

[REDACTED]

[REDACTED]

[REDACTED]

[REDACTED]

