4.3.2.1 Balovaptan (Oral Administration)

An oral dose of balovaptan 10 mg (Cohort 1) or 50 mg (Cohort 2) will be administered in the morning of Day 1 of Period 1 and each morning of Days 1 to 14 of Period 2. On Days 1 of Period 1 and Days 7 and 14 of Period 2, study drug administration will be after an overnight fast of at least 10 hours, followed by another 4 hours of fasting until lunch. On the other dosing days, study drug administration will take place at least 30 minutes before breakfast. Water will be allowed ad libitum until 1 hour prior to dosing and from 1 hour post dosing, and a maximum of 3 liters a day.

Study drug will be swallowed whole with 240 mL of still water.

4.3.2.2 [¹³C]-Labeled Balovaptan

On Day 1 of Period 1 and on Day 14 of Period 2, a single microdose of [¹³C]-labeled balovaptan 0.1 mg will be administered by a 15-minute constant IV infusion. The IV infusion will start 1.25 hours after administration of the oral dose of unlabeled balovaptan on Day 1 of Period 1 and Day 14 of Period 2.

Details on study drug preparation by the PRA Health Sciences (PRA) pharmacy will be described in the Manufacturing Batch Record, which will be prepared by the PRA pharmacy.

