Appendix 1 Schedule of Activities (cont.)

AE = adverse event; BMI = body mass index; CG = clinical genotyping; CRU = clinical research unit; [REDACTED]; C-SSRS = Columbia-Suicide Severity Rating Scale; D = Day; ECG = electrocardiogram; FSH = follicle-stimulating hormone; IV = intravenous; PK = pharmacokinetic.

- a Subjects will be admitted to the CRU on Day -1 and will be allowed to leave when all assessments on Day 10 have been completed. Subjects will return in the afternoon of Day 14 of Period 1 (which is also Day -1 of Period 2) and will be allowed to leave when all assessments on Day 19 have been completed.
- b The IV infusion of the microdose will start 1.25 hours after the oral study drug administration on Day 1 of Period 1 and Day 14 of Period 2.
- c On Day 1 of Period 1, and Days 7 and 14 of Period 2, subjects are fasted for at least 10 hours prior to dosing. Water will be allowed ad libitum until 1 hour prior to dosing and from 1 hour after dosing. No food is allowed for at least 4 hours postdose. Standardized lunch and dinner are provided 4 and 10 hours postdose, respectively, on Day 1 of Period 1, and Days 7 and 14 of Period 2. Standardized afternoon and evening snacks will be provided as well on these days.
On the other dosing days in the multiple dosing period, subjects will be dosed at least 30 minutes prior to breakfast. On these dosing days, meals will not be standardized.
- d All PK sampling times are relative to oral dosing (see also [Appendix 2](#)).
[REDACTED]
- f Includes measurement of height and BMI.
- g Triplicate ECGs will be collected at screening and Day -1 of Period 1 only. At all other time points a single ECG will be collected (Period 1: Day 10; Period 2: Day -1 of Period 2; predose on Days 6 and 11; Day 18 (96 hours after last dosing); follow-up).
- h Vital signs will be measured at screening (in triplicate), and in Period 1: on Day -1 (in triplicate), Day 1 at 3 hours postdose, Day 2, Day 5; in Period 2: on Day -1, predose on Days 1, 7 and 14; on Day 18 (96 hours after last dosing); follow-up. At screening and on Day -1 of Period 1, vital signs will be measured in triplicate; at other time-points, vital signs will be single measurements.
- i For females only: FSH and serum pregnancy test at screening, and serum pregnancy test only at all other time points.
- j Hematology samples will be collected at screening, Day -1 of Period 1, Day -1 of Period 2; predose on Days 6 and 11 of Period 2; Day 18; follow-up.

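### In Period 1 the [13C] tracer stops at 108 h while the same confined subjects are bled to 216 h, so the IV AUC0-inf behind the primary F may sit at or near the SAP's 20% extrapolation limit

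*Protocol*

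**What the plan says.** The sampling tables in Protocol Appendix 2 and SAP Appendix 3 agree. In Period 1 the last [13C]-balovaptan sample is in the row "108 (P1/D5 or P2/D18"). The 120, 144, 168, 192 and 216 h rows carry a mark only for unlabeled balovaptan and its metabolites. Protocol Section 3.1 keeps subjects in the unit for all of these draws: "In Period 1, subjects will be discharged on Day 10 after all assessments have been completed". In Period 2 both analytes stop at 108 h, so the mismatch is confined to Period 1.

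On timing, Protocol Appendix 1 states: "All PK sampling times are relative to oral dosing". Protocol Section 4.3.2.2 adds: "The IV infusion will start 1.25 hours after administration of the oral dose of unlabeled balovaptan". The tracer is "administered by a 15-minute constant IV infusion".

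SAP Table 1 computes F from AUC0-inf of both analytes, and CL as the tracer dose over its AUC0-inf. For AUC0-inf the table says: "Percent extrapolation less than or equal to 20% is required to obtain a reliable" value. Its programming note leaves the parameter out above that limit. SAP Section 16.2.2 excludes such parameters from descriptive statistics and says of the lambda-z points that "the range should ideally be spread over a time interval representing at least 2 half-lives".

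The only half-life is in Protocol Section 1.2.1.1: "the mean apparent elimination half-life after the last dose (Day 14) was approximately 46 hours".

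**The concern.** The two AUCs that form the primary ratio are observed over windows that differ two-fold, and the shorter window belongs to the denominator. A subject can have a complete oral profile and still lose the individual F because the tracer AUC0-inf fails the 20% rule. At the only documented half-life, a 108 h window lands almost exactly on that limit.

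The loss would not be random. It falls on subjects with long half-lives, and it may become visible only after bioanalysis, when those subjects already count as having completed all assessments to Day 10. The blood needed to avoid most of this is already being drawn. The readable text gives neither a reason for stopping the tracer at 108 h nor a tracer LLOQ.

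**Working it through.** **The plan's own figure.** Protocol Table 4 gives a precision factor of 1.50 for 6 subjects and 35% variability. It reproduces as exp(t(0.95, n-1) × 0.35 × √(2/n)): with n = 6, exp(2.015 × 0.35 × 0.577) = 1.50. The same formula gives 1.42 at 30% and 1.59 at 40%, as in the table. With 5 usable subjects at 35% it gives 1.60, and with 4 it gives 1.79. The figure is sound but presupposes 6 usable subjects.

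**Inputs from the documents.** Infusion start 1.25 h; duration T = 0.25 h (so it ends at 1.5 h); last tracer sample 108 h; last oral sample 216 h; extrapolation limit 20%; mean half-life 46 h; accumulation about 4-fold at 12 mg QD and 2-fold at 52 mg QD.

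**Assumptions.** Mono-exponential decline unless stated. Half-life range 24-58 h, the values implied by 2- and 4-fold accumulation at a 24 h interval if kinetics did not change with time: half-life = 24 × ln2 / [-ln(1 - 1/R)], giving 24.0 h and 57.8 h. Between-subject CV of half-life 20-40%, log-normal.

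**Extrapolated share.** With k = ln2/half-life, share = [(1 - exp(-kT))/(kT)] × exp(-k(tlast - 1.5)). At 46 h, k = 0.01507 per hour; at tlast = 108 h the share is 0.998 × exp(-1.605) = 20.1%. The window after infusion end is 106.5/46 = 2.3 half-lives.

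| Half-life | 108 h | 120 h | 144 h | 216 h |
|---|---|---|---|---|
| 24 h | 4.6% | 3.3% | 1.6% | 0.2% |
| 36 h | 12.8% | 10.2% | 6.4% | 1.6% |
| 46 h | 20.1% | 16.7% | 11.7% | 3.9% |
| 57.8 h | 27.9% | 24.1% | 18.1% | 7.6% |

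**Break-even half-life** (share = 20%): ln2 × (tlast - 1.375)/ln5. This is 45.9 h at 108 h, 51.1 h at 120 h, 61.4 h at 144 h and 92.4 h at 216 h.

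**Distribution phase.** If an early phase holds a fraction f of the IV AUC (assumed), the share is multiplied by (1 - f). At 46 h and 108 h it becomes 18.0% for f = 0.10 and 16.0% for f = 0.20. The 108 h break-even, ln2 × 106.625/ln((1 - f)/0.2), moves to 49.1 h and 53.3 h.

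**Chance that at least 6 of 8 pass.** The pass probability p is the log-normal probability of a half-life below break-even, with 46 h or 36 h entered as the arithmetic mean; the chance is the binomial tail for 8 subjects.

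- Mean 46 h, CV 20-40%, f = 0: p = 0.54-0.57, or 4.3-4.6 of 8 expected; chance 0.20-0.26.
- Same, f = 0.10: chance 0.41-0.47. Same, f = 0.20: 0.60-0.80.
- Mean 36 h, CV 35%: 0.82 with f = 0, 0.97 with f = 0.20.
- Mean 46 h, CV 20-40%, f = 0, tracer quantifiable to 144 h: 0.85-0.99. To 216 h: above 0.99.

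**The case against.** **The half-life belongs to another regimen.** The primary endpoint is single-dose, whereas 46 h is an oral mean after Day 14, and Protocol Section 3.3.2 describes the multiple-dose kinetics as time-dependent. This stands. A reader might infer that the tracer AUC is known to be cut off at the limit. The documents support only a projection, comfortable at 36 h and failing at 58 h. The ends of the range are weak too: a linear drug with a 46 h half-life would accumulate 1/(1 - exp(-0.01507 × 24)) = 3.3-fold, and the documents report 4-fold and 2-fold.

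**The chance of 6 of 8 is easily overstated.** Entering 46 h as a median gives 0.14, but the protocol calls it a mean. A distribution phase raises the chance a good deal. Both are reflected above.

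**The target of 6 is defined differently.** Protocol Section 6.1 counts subjects dosed and assessed to Day 10, not those passing the 20% rule, and Section 4.1 allows more enrolment if too few provide data. So the plan's stated target is not itself shown to be missed. What is at risk is the number with a usable individual F.

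**Loss from the model is not explicit.** The 90% CI comes from a mixed model on log CL and CL/F. Neither clearance row in SAP Table 1 carries an exclusion, and Section 16.2.2 speaks of descriptive statistics. The model also pools Days 1 and 14. This stands: individual F is dropped, but whether Day 1 CL leaves the model is open.

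**Bias.** A reader might infer that F would come out too low, because long half-life, low hepatic clearance and small first-pass loss may go together. That is plausible but neither quantified nor stated in the documents. Unequal windows alone do not bias AUC0-inf if lambda-z is well estimated, and the two-half-life span is an ideal that 2.3 half-lives can meet.

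**Assay sensitivity may explain 108 h.** Scaling the 484 ng/mL Cmax at 52 mg by 2-fold accumulation and by dose gives about 484/2 × 0.1/52 = 0.47 ng/mL at peak, 0.09 at 108 h and 0.02 at 216 h. This is rough, assuming dose-proportionality and IV levels like oral. The gain from the latest samples is therefore uncertain. The near ones are a smaller step: at 46 h the 120 and 144 h levels are 83% and 58% of the 108 h level.

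**Conclusion.** The point holds as a conditional design weakness. The schedule mismatch is certain. If the single-dose IV half-life is near 46 h, 16-20% of the tracer AUC0-inf is extrapolated, at or close to the limit above which AUC0-inf and the individual F are dropped. Under an assumed 20-40% CV, the chance of at least 6 of 8 valid tracer AUC0-inf values then runs from about 0.20 (mono-exponential) to 0.80 (20% distribution share). If the mean is 36 h with 35% CV, that chance is 0.82 or more and the problem is modest.

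The conclusion rests on an unstated half-life, an assumed spread and an unstated LLOQ. It does not establish that F is biased in a known direction, that the protocol's own target of 6 will be missed, or that subjects leave the mixed model. The change is still worth making: it protects the primary endpoint and uses draws already scheduled.

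**What to change.** In Protocol Appendix 2 and SAP Appendix 3, add the [13C]-balovaptan assay to the existing Period 1 draws after 108 h. Include at least 120 and 144 h, and go on through 168, 192 and 216 h as far as the tracer LLOQ allows. State the LLOQ, or the reason for stopping earlier.

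The Period 1 and Period 2 tracer windows would then differ, although their CL values enter one model. So also report Day 1 CL and F with the tracer truncated at 108 h, as a sensitivity analysis.

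Cost: up to 5 assays × 16 subjects = 80, with no new visit or sampling time. Plasma aliquot volume for the separate tracer method must be confirmed. Late samples may fall below the LLOQ, which reduces the gain. SAP Section 16.2.2 already sets such post-tmax values to missing when estimating parameters, so they would do little harm.
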